## **10 STATISTICAL CONSIDERATIONS**

The primary objective of this pilot trial is to preliminarily evaluate the efficacy of combining tremelimumab and durvalumab in patients with advanced HCC, either alone or with cryoablation, TACE, or RFA, and in patients with advanced biliary tract carcinoma (BTC), either alone or with cryoablation, or RFA.

Cohorts A1 and A2 will enroll patients with advanced HCC, BCLC stage B/C and cohort B will enroll patients with intra/extra-hepatic cholangiocarcinoma. Cohort A1 will have 1 treatment Arm 1 (one without any ablative procedure) and Cohort A2 will have 3 separate treatment arms of 10 patients apiece (one a piece with TACE, RFA, or cryoablation). Cohort B will have 3 separate treatment arms of 10 patients apiece (one without any ablative procedure, one with RFA, and one with cryoablation). The initial 10 patients in cohorts A1 and B, the treatment arms without ablative procedure, must have satisfactory safety and feasibility outcomes in order to permit the treatment arms with ablation to open. This will likely mean that 7 or more of 10 are able to result in complete treatment for the patients. For this pilot, the assignment to specific method of ablation will be done by the multidisciplinary tumor board and thus will not be done randomly. As such, the results must be treated as preliminary and exploratory, requiring independent confirmation of any potentially positive findings.

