As each of these 7 treatment arms of 10 patients will be considered a small pilot, each will have same statistical objective, and each of these arms will be evaluated for efficacy as follows. For both HCC and BTC there is no standard second-line therapy in the advanced setting. Based on historical data of investigational agents for both these diseases and stage (i.e. post-sorafenib HCC and post-gem/cis BTC) the 6-month PFS would be not greater than 10-15%[\[42, 43\]](#). In each treatment arm of 10 patients in cohorts A1, A2 and B, the trial will have 82% power to rule out 15% as the proportion stable at 6 month in favor of 50% being stable at 6 months, with each evaluation assuming that a one-sided 0.10 significance level exact binomial test would be performed. If there are 3 patients in 10 who are able to have stable disease at a 6 month evaluation, then the lower one-sided 90% confidence bound for 3/10 is 11.6% (the two sided 80% confidence interval extends from 11.6% to 55.2%). Similarly, with 4 in 10 with stable disease at 6 months, the lower one-sided 90% confidence bound for 4/10 is 18.8% (the two sided

80% confidence interval extends from 18.8% to 64.6%). Thus, in Cohorts A1, A2 or B, 3 or 4 patients out of 10 attaining stable disease at 6 months in any of the 7 treatment arms would tentatively rule out 10-15% as the fraction who would do so, with 90% one sided confidence. The results from the ablation treatment arms of cohort A2 (using TACE, RFA, or cryoablation) may also have their results combined in an exploratory fashion to report their overall efficacy. Similarly, the results from the ablation treatment arms of cohort B (using RFA or cryoablation) may also have their results combined in an exploratory fashion to report their overall efficacy.

Should positive findings be identified in any of the treatment arm of cohorts A1, A2 or cohort B, then after this pilot phase has been concluded, subsequent, more definitive evaluation may be conducted in the appropriate sub-cohorts using larger numbers of patients, as defined by amendments (or separate protocols if warranted) used to describe the expansion cohorts.

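### The 90% confidence that Section 10 attaches to 3 or 4 of 10 in any of seven arms holds only for one arm on its own, and against 15% only at 4/10 or more; the chance that some arm crosses by luck is not given

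*Combined protocol and SAP*

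**What the plan says.** Everything on this point is in Section 10 (Statistical Considerations).

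- The arms are set up as separate pilots: "As each of these 7 treatment arms of 10 patients will be considered a small pilot, each will have same statistical objective".
- The historical benchmark for both diseases is given as a range: "the 6-month PFS would be not greater than 10-15" per cent.
- The design claim is made arm by arm ("In each treatment arm of 10 patients in cohorts A1, A2 and B"). Its power is given as "82% power to rule out 15% as the proportion stable at 6 month in favor of 50% being stable at 6 months". The error rate is likewise set for one arm at a time, "with each evaluation assuming that a one-sided 0.10 significance level exact binomial test would be performed".
- Two worked results follow: a one-sided 90% lower bound of 11.6% for 3/10 and of 18.8% for 4/10.
- The conclusion drawn from them concerns a result of 3 or 4 out of 10: "in any of the 7 treatment arms would tentatively rule out 10-15% as the fraction who would do so, with 90% one sided confidence".
- Its consequence is worded the same way: "Should positive findings be identified in any of the treatment arm of cohorts A1, A2 or cohort B", a larger evaluation may follow by amendment or separate protocol.
- Earlier in the section, because the ablation method is not assigned at random, "the results must be treated as preliminary and exploratory, requiring independent confirmation of any potentially positive findings". The ablation arms open only if the two drug-only arms have satisfactory safety and feasibility.

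No error rate across arms is stated, and no definition of success for the pilot as a whole.

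**The concern.** The concluding sentence makes one confidence statement do two jobs.

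First, it joins two counts (3 and 4) to two benchmark values (10% and 15%) without saying which count excludes which value. Read literally, 3/10 excludes 15%, and the plan's own bound of 11.6% contradicts that.

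Second, it extends the statement across seven arms. The 0.10 level and both lower bounds are calculated for one arm fixed in advance. They do not describe an arm singled out because it was the one that crossed, and the section never says how often at least one arm would cross by chance.

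The pilot is meant to point to arms worth larger study. A reader who takes the sentence at face value would report a 3/10 arm as having excluded 15%. The same reader would take one positive arm among seven as stronger evidence than it is.

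**Working it through.** **Inputs, all from Section 10.** n = 10 per arm; seven arms; benchmark 10% to 15%, with 15% used for power; alternative 50%; one-sided 0.10 exact binomial test per arm.

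**Step 1. Reproduce the plan's figures.** The cutoff is the smallest r with P(X ≥ r | n = 10, p = 0.15) ≤ 0.10.

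- P(X ≥ 3 | 0.15) = 0.1798, which is above 0.10.
- P(X ≥ 4 | 0.15) = 0.0500, which is below 0.10. The cutoff is therefore 4/10.
- Power at 50%: P(X ≥ 4 | 0.50) = 1 − (1 + 10 + 45 + 120)/1024 = 848/1024 = 82.8%. The stated 82% belongs to the 4/10 cutoff. A 3/10 cutoff would have 94.5%.
- Exact (Clopper-Pearson) one-sided 90% lower bounds are 11.6% for 3/10 and 18.8% for 4/10. Both match.

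**Step 2. Which count excludes which value.**

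| Result | Lower 90% bound | Per-arm error at 10% | Per-arm error at 15% | Excludes 10%? | Excludes 15%? |
|---|---|---|---|---|---|
| 3/10 | 11.6% | 7.0% | 18.0% | yes | no |
| 4/10 | 18.8% | 1.3% | 5.0% | yes | yes |

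**Step 3. Chance that at least one arm crosses.** Different patients are in each arm, so with a common true rate the counts are independent. For k arms opened and per-arm error a, the chance is 1 − (1 − a)^k.

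Seven arms:

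- 3/10 at 15%: 1 − (1 − 0.1798)^7 = 75.0%
- 3/10 at 10%: 1 − (1 − 0.0702)^7 = 39.9%
- 4/10 at 15%: 1 − (1 − 0.0500)^7 = 30.2%
- 4/10 at 10%: 1 − (1 − 0.0128)^7 = 8.6%

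Two drug-only arms:

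- 3/10: 13.5% at a true 10%, 32.7% at 15%
- 4/10: 2.5% at a true 10%, 9.7% at 15%

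**Step 4. Separate the two causes.** At a true 15% with seven arms, moving from 4/10 to 3/10 raises the any-arm chance by 75.0 − 30.2 = 44.8 percentage points. That part comes from the cutoff. Holding the cutoff at 4/10, going from one arm to seven takes 5.0% to 30.2%, and that part is multiplicity.

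**The case against.** The strongest reply is that the plan has no any-arm success rule. Each arm is its own pilot, the 0.10 level is tied to each evaluation, and the phrase about any of the seven arms can be taken to mean whichever arm it happens in. On that reading, and if 3/10 is paired with 10% and 4/10 with 15%, the sentence is correct arm by arm. Further evaluation is optional, the wording is tentative, and independent confirmation is required whatever the reason for a positive finding.

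Most of this stands. A reader might infer that the pilot declares success when any arm reaches 3/10, and so gives a false success 75% of the time. The documents do not support that. No trial-level success is defined, and no expansion is automatic. The 75% needs all seven arms open, although five depend on the drug-only results, and a true rate at the top of a 10% to 15% benchmark. Much of it comes from the 3/10 cutoff and not from the number of arms. At 4/10 with a true 10%, the seven-arm chance is 8.6%, below the nominal 10%. Treating seven arms as one family is also a choice, because they span two diseases. At 4/10 and 15% the figures are 18.5% for the four HCC arms, 1 − 0.950^4, and 14.3% for the three BTC arms, 1 − 0.950^3.

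What does not stand is that the caveats cure the sentence. The call for confirmation follows from non-random assignment. It neither tells the reader which count excludes 15% nor gives the chance of a lucky arm. The pairing of counts with benchmark values is something the reader has to supply.

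**Conclusion.** The sentence needs correcting; the design does not. The 90% is a per-arm figure. Against 15% it is met at 4/10 or more; 3/10 excludes only the lower end of the benchmark.

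The missing any-arm chance is 9% to 30% at 4/10 and 40% to 75% at 3/10 with seven arms, and 2.5% to 10% and 14% to 33% with two. These figures assume independent arms of exactly 10 evaluable patients and a common true rate between 10% and 15%. A lower true rate would reduce them.

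A reader might go further and require 5/10 of any arm picked from the seven. Simultaneous (Sidak) 90% lower bounds over seven arms are 5.5%, 10.5% and 16.5% for 3, 4 and 5 of 10, so only 5/10 clears 15% on that scale. Power at a true 50% would then fall from 82.8% to 62.3%. For separate exploratory arms in two diseases that is a trade-off, and nothing in the plan obliges the sponsor to make it.

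**What to change.** Replace the concluding sentence in Section 10 with text to this effect:

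*For a single arm considered on its own, 4 or more of 10 excludes 15% with one-sided 90% confidence; 3 of 10 excludes 10% but not 15%. If no arm is better than the 10% to 15% benchmark, the chance that at least one arm reaches 4 of 10 is 9% to 30% with seven arms open and 2.5% to 10% with the two drug-only arms only; for 3 of 10 it is 40% to 75% and 14% to 33%.*

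In the report, give the same chance for the number of arms actually opened, using 1 − (1 − a)^k. A simultaneous bound may be shown beside the single-arm bound as an optional extra, but should not become the standard for calling an arm positive.

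The cost is a few sentences and one line in the results. The per-arm test, its 82% power, the number of patients and all procedures are unchanged. The only loss is that a 3/10 arm can no longer be described as excluding 15%.

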## Arms

Number	Name	Description
1	A1	Durvalumab + Tremelimumab
2	A2	Durvalumab + Tremelimumab + TACE
3	A3	Durvalumab + Tremelimumab + RFA
4	A4	Durvalumab + Tremelimumab + Cryo

Subjects in cohort A1 will be directly assigned to arm A1.

Subjects in cohort A2 will be directly assigned to arms A2, A3 or A4 per consultation with the interventional radiologists. The reason for this is that there are technical considerations (size and location of lesion, main portal vein occlusion etc.) which would make one procedure preferable over the other. 10 evaluable subjects will be assigned to each intervention.

The first 10 subjects in cohort B will be directly assigned to arm A1.

The remaining subjects in Cohort B will be directly assigned to arms A3 or A4 per consultation with the interventional radiologists. The reason for this is that there are technical considerations (size and location of lesion, main portal vein occlusion etc.) which would make one procedure preferable over the other. 10 evaluable subjects will be assigned to each intervention.

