### 6.3.1 Definitions

Evaluable for toxicity: All patients will be evaluable for toxicity from the time of their first treatment with tremelimumab and durvalumab.

Evaluable for objective response: Only those patients who have measurable disease present at baseline, have received at least one cycle of therapy, and have had their disease re-evaluated will be considered evaluable for response. These patients will have their response classified according to the definitions stated below. (Note: Patients who exhibit objective disease progression prior to the end of cycle 1 will also be considered evaluable.)

Evaluable Non-Target Disease Response: Patients who have lesions present at baseline that are evaluable but do not meet the definitions of measurable disease, have received at least one cycle of therapy, and have had their disease re-evaluated will be considered evaluable for non-target disease. The response assessment is based on the presence, absence, or unequivocal progression of the lesions.

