It is expected that up to 2 patients per month may be able to enroll onto this trial. Cohort A1 will require 10 evaluable patients, Cohort A2 may require up to 30 evaluable patients and cohort B may require up to 30 evaluable patients. The accrual ceiling for the protocol will be set at 90 patients to allow for a small number of inevaluable patients to be enrolled. Thus, it is expected that 24-36 months may be needed to accrue all patients onto this trial.

To address safety and feasibility of combining tremelimumab and durvalumab in (Cohorts A1 and A2) patients with advanced HCC (either alone or with cryoablation, TACE or RFA) and (Cohort B) in patients with advanced biliary tract carcinoma (BTC) (either alone or with cryoablation or RFA), adverse events will be tabulated by grade per CTCAE 4 and analyzed and reported descriptively.

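### Section 10 names no analysis set for 6-month PFS and fills arms to evaluable patients, so a dosed patient lost before any repeat scan could leave the denominator

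*Combined protocol and SAP*

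**What the plan says.** Section 10 sets one exact binomial test per arm of 10, one-sided at 0.10, with 82% power for 50% against 15%. The benchmark is historical: "the 6-month PFS would be not greater than 10-15" percent. It reads a result of "3 or 4 patients out of 10 attaining stable disease at 6 months in any of the 7 treatment arms would tentatively rule out" that benchmark, and says a positive arm may lead to a larger evaluation.

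Enrolment is counted in evaluable patients. Section 10 says "Cohort A1 will require 10 evaluable patients, Cohort A2 may require up to 30 evaluable patients", with up to 30 more in cohort B, and adds: "The accrual ceiling for the protocol will be set at 90 patients to allow for a small number of inevaluable patients to be enrolled". For the ablation arms, section 2.3.1 says "10 evaluable subjects will be assigned to each intervention". The drug-only arm of cohort B is described there simply as the first 10 subjects.

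No section says who is evaluable for PFS. Section 6.3.1 defines the term for toxicity (all treated patients), for objective response and for non-target disease. For objective response, patients with measurable disease who "have received at least one cycle of therapy, and have had their disease re-evaluated will be considered evaluable for response". A note adds: "Patients who exhibit objective disease progression prior to the end of cycle 1 will also be considered evaluable". Section 10 does not refer to section 6.3.1.

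**The concern.** If the response definition is carried over to PFS, one kind of patient falls outside it: someone who has been dosed but dies, deteriorates clinically without objective progression, or is lost before any repeat scan. The note protects only early objective progression, and routine re-evaluation is every 8 weeks. An arm filled to 10 evaluable patients could then take a replacement for that patient.

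Most such patients would be PFS failures. Removing them raises the observed rate, and because the comparator is a fixed figure, no control arm loses patients in the same way. In an arm of 10, a few patients can decide whether the arm counts as positive and is taken forward. Two analysts working from this text could report different denominators for the same arm.

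**Working it through.** **Inputs.** From section 10: n = 10 per arm, null 15% (benchmark range 10-15%), alternative 50%, one-sided alpha 0.10, positive reading at 3 or 4 of 10, 10 + 30 + 30 = 70 evaluable patients, ceiling 90. From section 1.2.10: 4 of 32 HCC patients in the predecessor study were classed as unevaluable, which is 12.5%. The share dropped, d, and the outcomes of dropped patients in this trial are assumptions.

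**Plan's own figures.** P(X ≥ 4 | 10, 0.15) = 0.050 and P(X ≥ 4 | 10, 0.50) = 0.828, so the stated 82% power belongs to the rule of at least 4/10. Exact lower one-sided 90% bounds are 11.6% for 3/10 and 18.8% for 4/10, as stated. Against 10%, P(X ≥ 3 | 10, 0.10) = 0.070.

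**Effect of dropping failures.** If a share d of dosed patients is dropped and all of them are failures, a true all-dosed rate p becomes p/(1 − d) among those kept. For example, 0.15/(1 − 0.125) = 0.1714. Type I error is the binomial tail at that rate:

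| Dropped | ≥4/10, true rate 15% | ≥3/10, true rate 10% |
|---|---|---|
| 0 | 5.0% | 7.0% |
| 12.5% (4/32) | 7.6% | 9.7% |
| 20% | 10.0% | 12.0% |
| 22.2% (20/90, all spare places) | 10.9% | 12.8% |

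The first rule passes 0.10 at 20.0% dropped, the second at 13.7%.

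**If not all dropped patients fail.** With a fraction f failing, the rate among those kept is [p − d(1 − f)]/(1 − d). For p = 0.15 and f = 0.90, the error for ≥4/10 is 5.8% at 12.5% dropped and 6.4% at 20%. At f = 0.85 there is no bias, and below that it is downward.

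**A single arm.** Put the replaced failures back in the denominator and recompute the lower bound:

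- 3/10: 11.6%; 3/11: 10.5%; 3/12: 9.6%, which no longer excludes 10%.
- 4/10: 18.8%; 4/11: 16.9%; 4/12: 15.4%; 4/13: 14.2%, which no longer excludes 15%.

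One replaced failure changes neither reading. It takes two against 10% and three against 15%.

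**Power with 10 dosed patients.** At ≥4/10 it is 82.8% if 50% is an all-dosed rate. If 50% was meant for evaluable patients, the all-dosed rate at 12.5% dropped is 0.50 × 0.875 = 0.4375 and power is 70.7%.

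**The case against.** The strongest reply is that replacement is inferred. A reader might conclude that the protocol directs early failures to be replaced, and it does not. Section 6.3.1 is written for response, section 10 does not invoke it, and death is ordinarily an event in PFS. Inevaluable could also mean enrolled but never dosed, and section 10 expects only a small number. This stands as a limit on the point. It does not settle whom to count, because no other definition is offered.

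Other text narrows the gap. The table note in section 6.3.4.3 asks for efforts to document progression after clinical deterioration, and Appendix E expects tumor assessments to continue after a stop for reasons other than progression. Neither assigns an outcome to a patient who is never scanned again.

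The predecessor rate transfers poorly. Its 4 of 32 came off for toxicity or progression, and the present note would keep early objective progressors. Section 1.2.10 also describes a patient taken off for pneumonitis who was disease-free at 16 months, so dropped patients are not all failures. The 12.5% is therefore only a reference value.

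The benchmark may itself be a rate among evaluable patients. The documents do not say. If it is, an evaluable-only comparison is like for like and the inflation shown above disappears.

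Lastly, section 10 says "the results must be treated as preliminary and exploratory" and asks for independent confirmation. That lowers the stakes but does not fix the denominator.

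**Conclusion.** The gap holds, at moderate size. The primary endpoint has no analysis set, enrolment is counted with an undefined term, and the nearest definition would leave out some early failures. The upward bias depends on three assumptions: that such patients are in fact replaced, that most of them are failures, and that 10-15% is an all-treated rate.

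Two stronger readings are not supported. A reader might infer that the test breaks its 0.10 level. For at least 4/10 against 15%, the rule behind the stated power, it stays within 0.10 up to about 20% dropped even when every dropped patient fails. Only the weaker reading, 3/10 against 10%, passes 0.10 sooner. A reader might also infer that a single replaced patient can overturn a result, and the bounds show that it cannot. The stated power and confidence bounds are correct as calculated.

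**What to change.** In section 10:

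1. Make all patients who receive a first dose the primary denominator for 6-month PFS, and replace only patients never dosed. Each arm then closes at 10 dosed, with at least 4/10 needed against 15% and at least 3/10 against 10%.
2. Count death or RECIST 1.1 progression by 6 months as failure, a progression-free scan at or after 6 months as success (on or off treatment), and no assessment at or after 6 months as failure. Report a Kaplan-Meier estimate with its confidence interval alongside.
3. Report, as sensitivity analyses, an evaluable set with its definition and the reason for each exclusion and, for the five ablation arms, a set of patients who received the procedure, since some will stop before Day 36.
4. If accrual overshoots, use the exact cut-off for the number dosed. Against 15%: at least 4 for 11-12 and at least 5 for 13-14. Against 10%: at least 3 for 11 and at least 4 for 12-14.
5. State whether the 50% target and the 10-15% benchmark are all-dosed rates.

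The change is wording only, with no added visits or scans. Reported rates will be slightly lower. A patient who stops for toxicity and is never scanned again counts as a failure even if progression-free, and the Kaplan-Meier estimate shows how much that matters. Power is 83% with 10 dosed if 50% is an all-dosed rate, but about 71% at 12.5% dropped if it was meant for evaluable patients. Section 10 should say so.

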#### 3.4.2.4 Hepatic function abnormalities (hepatotoxicity)

Hepatic function abnormality is defined as any increase in ALT or AST to greater than  $3 \times$  ULN and concurrent increase in total bilirubin to be greater than  $2 \times$  ULN. Concurrent findings are those that derive from a single blood draw or from separate blood draws taken within 8 days of each other. Follow-up investigations and inquiries will be initiated promptly by the investigational site to determine whether the findings are reproducible and/or whether there is objective evidence that clearly supports causation by a disease (e.g., cholelithiasis and bile duct obstruction with distended gallbladder) or an agent other than the IP. Guidelines for management of patients with hepatic function abnormality are provided in [Appendix F](#).

Due to the fact that in HCC patients elevated transaminase and/or bilirubin levels are common and fluctuant as a result of underlying liver disease (e.g. viral hepatitis), the toxicity criteria outlined in [Appendix F](#) will be interpreted with the following caveats:

- 1) For patients with HCC with normal liver transaminases and/or bilirubin at baseline, the criteria apply as outlined in [Appendix F](#). (i.e. if a grade 2 event occurs treatment will be held until resolution to grade 1)
- 2) For patients with HCC who have elevated liver transaminases and/or bilirubin at baseline (grade 1 or 2 i.e. still allowing for study entry), subsequent occurrences of grade 2 elevations will not result in holding of therapy.
- 3) Grade 3 events will be treated as per [Appendix F](#) irrespective of baseline levels.

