## 6.5 TOXICITY CRITERIA

The following adverse event management guidelines are intended to ensure the safety of each patient while on the study. The descriptions and grading scales found in the revised NCI Common Terminology Criteria for Adverse Events (CTCAE) version 4.0 will be utilized for AE reporting. All appropriate treatment areas should have access to a copy of the CTCAE version 4.0. A copy of the CTCAE version 4.0 can be downloaded from the CTEP web site ([http://ctep.cancer.gov/protocolDevelopment/electronic\\_applications/ctc.htm#ctc\\_40](http://ctep.cancer.gov/protocolDevelopment/electronic_applications/ctc.htm#ctc_40)).

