#### 8.1.4 Severity

The severity of each Adverse Event will be assessed utilizing the CTCAE version 4.0.

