**The following variables will be collected for each AE:**

- AE (CTCAE version 4.0)
- The date and time when the AE started and stopped
- Changes in NCI CTCAE grade and the maximum CTC grade attained
- Whether the AE is serious or not
- Investigator causality rating against durvalumab or tremelimumab (yes or no)
- Action taken with regard to durvalumab + tremelimumab/ combination agent
- Outcome

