
Drug administration modifications of study drug/study regimen will be made to manage potential immune-related AEs based on severity of treatment-emergent toxicities graded per NCI CTCAE v5.0.
 
In addition to the criteria for permanent discontinuation of study drug/study regimen based on CTC grade/severity (table below), permanently discontinue study drug/study regimen for the following conditions:
 
 
• Inability to reduce corticosteroid to a dose of <math>\leq 10</math> mg of prednisone per day (or equivalent) within 12 weeks of the start of the immune-mediated adverse event (imAE)
 
• Grade 3 recurrence of a previously experienced treatment-related imAE following resumption of dosing
 
 
Grade 1 No dose modification
 
Grade 2 Hold study drug/study regimen dose until Grade 2 resolution to Grade <math>\leq 1</math>.
 
If toxicity worsens, then treat as Grade 3 or Grade 4.
 
Study drug/study regimen can be resumed once event stabilizes to Grade <math>\leq 1</math> after completion of steroid taper.
 
Patients with endocrinopathies who may require prolonged or continued steroid replacement can be retreated with study drug/study regimen on the following conditions:
 
 
1. The event stabilizes and is controlled.
 
2. The patient is clinically stable as per Investigator or treating physician's clinical judgement.
 
3. Doses of prednisone are at <math>\leq 10</math> mg/day or equivalent.
 
	
It is recommended that management of immune-mediated adverse events (imAEs) follows the guidelines presented in this table:
 
 
– It is possible that events with an inflammatory or immune mediated mechanism could occur in nearly all organs, some of them not noted specifically in these guidelines.
 
– Whether specific immune-mediated events (and/or laboratory indicators of such events) are noted in these guidelines or not, patients should be thoroughly evaluated to rule out any alternative etiology (e.g., disease progression, concomitant medications, and infections) to a possible immune-mediated event. In the absence of a clear alternative etiology, all such events should be managed as if they were immune related. General recommendations follow.
 
– Symptomatic and topical therapy should be considered for low-grade (Grade 1 or 2, unless otherwise specified) events.
 
– For persistent (<math>>3</math> to 5 days) low-grade (Grade 2) or severe (Grade <math>\geq 3</math>) events, promptly start prednisone 1 to 2 mg/kg/day PO or IV equivalent.
 
– Some events with high likelihood for morbidity and/or mortality – e.g., myocarditis, or other similar events even if they are not currently noted in the guidelines – should progress rapidly to high dose IV corticosteroids (methylprednisolone at 2 to 4 mg/kg/day) even if the event is Grade 2, and if clinical suspicion is high and/or there has been clinical confirmation. Consider, as necessary, discussing with the study physician, and promptly pursue specialist consultation.
 
– If symptoms recur or worsen during corticosteroid tapering (28 days of taper), increase the corticosteroid dose (prednisone dose [e.g., up to 2 to 4 mg/kg/day PO or IV equivalent]) until stabilization or improvement of symptoms, then resume corticosteroid tapering at a slower rate (<math>>28</math> days of
 

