AE Adverse event; CTC Common Toxicity Criteria; CTCAE Common Terminology Criteria for Adverse Events; imAE immune-mediated adverse event; IV intravenous; NCI National Cancer Institute; PO By mouth.

Specific Immune-Mediated Reactions				
Adverse Events	Severity Grade of the Event (NCI CTCAE version 5.0)	Dose Modifications	Toxicity Management	
Pneumonitis/Interstitial Lung Disease (ILD)	Any Grade	General Guidance	
For Any Grade:
 
 
Monitor patients for signs and symptoms of pneumonitis or ILD (new onset or worsening shortness of breath or cough). Patients should be evaluated with imaging and pulmonary function tests, including other diagnostic procedures as described below.
 
Suspected pneumonitis should be confirmed with radiographic imaging and other infectious and disease-related aetiologies excluded, and managed as described below
 
Initial work-up may include clinical evaluation, monitoring of oxygenation via pulse oximetry (resting and exertion), laboratory work-up, and high- resolution CT scan.
 
Consider Pulmonary and Infectious Disease Consults
 
	
	Grade 1 (asymptomatic, clinical or diagnostic observations only; intervention not indicated)	No dose modifications required. However, consider holding study drug/study regimen dose as clinically appropriate and during diagnostic work-up for other etiologies.	
For Grade 1 (radiographic changes only):
 
 
Monitor and closely follow up in 2 to 4 days for clinical symptoms, pulse oximetry (resting and exertion), and laboratory work-up and then as clinically indicated.
 
Consider Pulmonary and Infectious Disease consults.
 
	

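### The safety table uses CTCAE 4.0 while Appendix F's graded dose rules use 5.0, and section 3.4.2.4 conflicts with Appendix F's liver rules for HCC patients

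*Combined protocol and SAP*

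**What the plan says.** **Recording and analysis use version 4.0.** Section 6.5 states that "Common Terminology Criteria for Adverse Events (CTCAE) version 4.0 will be utilized for AE reporting". Section 8.1.4 states: "The severity of each Adverse Event will be assessed utilizing the CTCAE version 4.0". Appendix E opens its list of variables for each event with "AE (CTCAE version 4.0". Section 10 adds that "adverse events will be tabulated by grade per CTCAE 4 and analyzed and reported descriptively".

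**Graded dose actions use version 5.0.** The general part of Appendix F modifies drug administration "based on severity of treatment-emergent toxicities graded per NCI CTCAE v5.0". Its tables for specific immune-mediated, infusion-related and non-immune-mediated reactions carry the column heading "Severity Grade of the Event (NCI CTCAE version 5.0". Section 3.4.1 sends dose modification for immune-mediated events to Appendix F, and section 3.8.1 ties removal from therapy to section 3.4.

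**Liver events in HCC.** Section 3.4.2.4 gives three caveats for reading Appendix F, and none names a CTCAE version:
- Caveat 1: with normal baseline values Appendix F applies, explained as a hold for a grade 2 event until it is back to grade 1.
- Caveat 2: with grade 1 or 2 elevation at baseline, "subsequent occurrences of grade 2 elevations will not result in holding of therapy".
- Caveat 3: grade 3 events follow Appendix F whatever the baseline.

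Appendix F's general hepatitis rows are graded, but they direct HCC patients to a shaded block reserved for HCC. That block works in multiples of ULN or of baseline and contains no grades.

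**The concern.** Safety and feasibility form the secondary objective, and the only safety analysis in section 10 is a descriptive table by grade. A reader who wants to see why treatment was held or stopped will turn to that table, which names a different scale from the one behind the graded dose rules.

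The HCC liver rules raise a more practical problem. Two clinicians who each follow the text could act differently on the same laboratory value. Holds, exposure and time on treatment in the HCC arms would then depend partly on which section was consulted, and the data would not show which one it was.

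**Working it through.** There is no figure in the plan to reproduce, so the check sets the passages side by side.

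**1. Versions.** Four places name version 4.0: sections 6.5, 8.1.4 and 10, and Appendix E. Four parts of Appendix F name version 5.0: the general rules and the three reaction tables. No place converts one version to the other, asks for both grades, or says which prevails. The version 4.0 cut-points are not printed, so the number of events graded differently cannot be derived.

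**2. One ALT value under both liver rules.** Take an HCC patient with normal baseline liver tests whose ALT rises to 4 times ULN. Assume bilirubin is not rising and there is no sign of hepatic decompensation, so the rise is isolated.
- Appendix F, general rows, normal baseline: grade 2 is above 3.0 and up to 5.0 times ULN. Since 3.0 < 4 ≤ 5.0, this is grade 2.
- Section 3.4.2.4, caveat 1: a grade 2 event is held until grade 1. On the general rows that means 3.0 times ULN or less.
- Appendix F, HCC block, first row: above ULN and up to 5.0 times ULN, whatever the baseline. Since 1 < 4 ≤ 5.0, there is no dose modification unless the investigator judges the rise a significant worsening.

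The example is not a boundary case. The whole grade 2 transaminase band for a normal baseline (above 3.0 to 5.0 times ULN) lies inside the block's no-modification row (above 1 to 5.0 times ULN).

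**3. Release from a hold.** Caveat 1 ends the hold at grade 1, which is 3.0 times ULN on the general rows. Where the HCC block does impose a hold, its threshold for resolution is 5.0 times ULN. Values between 3.0 and 5.0 are therefore still unresolved under one passage and resolved under the other.

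**4. Caveats 2 and 3.** Both turn on grade 2 or grade 3 events, and the HCC block defines neither. A reader has to borrow the grades from the general rows, from which HCC patients have been directed away, or from version 4.0, which is not printed.

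**5. Patients concerned.** Section 10 plans 10 evaluable patients in cohort A1, up to 30 in A2 and up to 30 in B. HCC patients number 10 + 30 = 40 of 70 (57%). The share who will have an isolated AST or ALT between 3.0 and 5.0 times ULN from a normal baseline is not given.

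**The case against.** The strongest reply is that everything to do with recording and tabulating names version 4.0, so the safety table is coherent in itself, and Appendix F is a separately dated management guideline. That is right as far as it goes. It does not remove the difference in scale between the table and the graded dose rules.

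A reader might also infer more than the documents support:
- **That the grades will differ.** No event term is shown to be graded differently in the two versions, and many may coincide.
- **That version 5.0 grades drive every hold.** They do not. The HCC liver block uses multiples of ULN or baseline, the infusion-reaction rule in section 3.3.3 names no version, and the interruption rule in section 8.5.2.2 uses a combined transaminase and bilirubin definition.
- **That only one grade per event is kept.** Appendix E also collects changes in grade, the maximum grade and the action taken with study drug. Liver tests are scheduled weekly through cycle 4 and on day 1 of later cycles, so liver events could be regraded from the values. Events graded on clinical description have no such route.
- **That the version gap can be sized from Appendix F.** ALT rising from 4 to 10 times ULN is 10/4 = 2.5 times baseline: grade 1 on the abnormal-baseline rows and grade 3 on the normal-baseline rows. Both sets of rows are version 5.0, and the second does not apply to this patient, so the contrast says nothing about version 4.0. For an HCC patient the value falls in an ungraded row.
- **That the opening of the ablation arms is affected.** Section 10 ties this to satisfactory safety and feasibility, likely 7 or more of 10 completing treatment. No CTCAE grade enters the rule.

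On the liver conflict, it can be argued that section 3.4.2.4 is written as a reading of Appendix F and so prevails. But caveat 1 says that Appendix F applies as it stands, which leads back to the HCC block. The text does not settle which passage governs.

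**Conclusion.** The plan is wrong as written on two linked matters, both modest.

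First, the safety table and Appendix F's graded dose rules name different CTCAE versions with nothing to connect them. Tabulated grades need not match the grades behind dose actions, and the extent of any mismatch cannot be computed from the documents.

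Second, for HCC patients with normal baseline liver tests, section 3.4.2.4 and Appendix F give opposite hold instructions across the whole range above 3.0 to 5.0 times ULN for an isolated transaminase rise. This rests on reading the unversioned grade 2 of section 3.4.2.4 on Appendix F's general rows, and on the investigator not judging the rise a significant worsening. It can concern up to 40 of the 70 planned evaluable patients, with the actual number unknown.

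The power and confidence bounds in section 10 use no toxicity grade and are unaffected.

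**What to change.** The sponsor must reconcile section 3.4.2.4 with Appendix F's HCC liver block, so that each transaminase value leads to one instruction for holding and one for resuming. All three caveats should use terms that the block defines. No view is taken here on which rule is right.

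For the safety data there are two options:
- Name one CTCAE version throughout sections 6.5, 8.1.4 and 10 and Appendices E and F. No view is taken on which version.
- Keep version 4.0 for the table. For each event that led to a hold or discontinuation, record the Appendix F grade or threshold that was applied beside the version 4.0 grade, and state in section 10 which one is tabulated.

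The first option is a wording change, although events already graded under another version would need regrading. The second adds one field, and only for events with a dose action.
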